10.3.2. Definition of SAE

If an event is not an AE per definition above, then it cannot be an SAE even if serious conditions are met (eg, hospitalization for signs/symptoms of the disease under study, death due to progression of disease).

An SAE is defined as any untoward medical occurrence that, at any dose:
a. Results in death
b. Is life-threatening
The term "life-threatening" in the definition of "serious" refers to an event in which the participant was at risk of death at the time of the event. It does not refer to an event that hypothetically might have caused death if it were more severe.
c. Requires inpatient hospitalization or prolongation of existing hospitalization
In general, hospitalization signifies that the participant has been detained (usually involving at least an overnight stay) at the hospital or emergency ward for observation and/or treatment that would not have been appropriate in the physician's office or outpatient setting. Complications that occur during hospitalization are AEs. If a complication prolongs hospitalization or fulfills any other serious criteria, the event is serious. When in doubt as to whether "hospitalization" occurred or was necessary, the AE

should be considered serious.

Hospitalization for elective treatment of a preexisting condition that did not worsen from baseline is not considered an AE.

d. Results in persistent disability/incapacity

- The term disability means a substantial disruption of a person's ability to conduct normal life functions.
- This definition is not intended to include experiences of relatively minor medical significance such as uncomplicated headache, nausea, vomiting, diarrhea, influenza, and accidental trauma (eg, sprained ankle) which may interfere with or prevent everyday life functions but do not constitute a substantial disruption.

e. Is a congenital anomaly/birth defect

f. Other situations:

- Medical or scientific judgment should be exercised in deciding whether SAE reporting is appropriate in other situations such as important medical events that may not be immediately life-threatening or result in death or hospitalization but may jeopardize the participant or may require medical or surgical intervention to prevent one of the other outcomes listed in the above definition. These events should usually be considered serious.
- Examples of such events include invasive or malignant cancers, intensive treatment in an emergency room or at home for allergic bronchospasm, blood dyscrasias or convulsions that do not result in hospitalization, or development of drug dependency or drug abuse.
- Suspected transmission via a Pfizer product of an infectious agent, pathogenic or non-pathogenic, is considered serious. The event may be suspected from clinical symptoms or laboratory findings indicating an infection in a patient exposed to a Pfizer product. The terms "suspected transmission" and "transmission" are considered synonymous. These cases are considered unexpected and handled as serious expedited cases by pharmacovigilance personnel. Such cases are also considered for reporting as product defects, if appropriate.

10.3.3. Recording/Reporting and Follow-up of AEs and/or SAEs

AE and SAE Recording/Reporting		
The table below summarizes the requirements for recording adverse events on the CRF and for reporting serious adverse events on the CT SAE Report Form to Pfizer Safety. These requirements are delineated for 3 types of events: (1) SAEs; (2) nonserious adverse events (AEs); and (3) exposure to the study intervention under study during pregnancy or breastfeeding, and occupational exposure.		
It should be noted that the CT SAE Report Form for reporting of SAE information is not the same as the AE page of the CRF. When the same data are collected, the forms must be completed in a consistent manner. AEs should be recorded using concise medical terminology and the same AE term should be used on both the CRF and the CT SAE Report Form for reporting of SAE information.		
Safety Event	Recorded on the CRF	Reported on the CT SAE Report Form to Pfizer Safety Within 24 Hours of Awareness
SAE	All	All
Nonserious AE	All	None
Exposure to the study intervention under study during pregnancy or breastfeeding, and occupational exposure	All AEs/SAEs associated with exposure during pregnancy or breastfeeding Occupational exposure is not recorded.	All (and EDP supplemental form for EDP) Note: Include all SAEs associated with exposure during pregnancy or breastfeeding. Include all AEs/SAEs associated with occupational exposure.

When an AE/SAE occurs, it is the responsibility of the investigator to review all documentation (eg, hospital progress notes, laboratory reports, and diagnostic reports) related to the event.The investigator will then record all relevant AE/SAE information in the CRF.It is not acceptable for the investigator to send photocopies of the participant's medical records to Pfizer Safety in lieu of completion of the CT SAE Report Form/AE/SAE CRF page.There may be instances when copies of medical records for certain cases are requested by Pfizer Safety. In this case, all participant identifiers, with the exception of the participant number, will be redacted on the copies of the medical records before submission to Pfizer Safety.The investigator will attempt to establish a diagnosis of the event based on signs, symptoms, and/or other clinical information. Whenever possible, the diagnosis (not		

the individual signs/symptoms) will be documented as the AE/SAE.

Assessment of Intensity

The investigator will make an assessment of intensity for each AE and SAE reported during the study and assign it to 1 of the following categories:

- **Mild:** An event that is easily tolerated by the participant, causing minimal discomfort and not interfering with everyday activities.
- **Moderate:** An event that causes sufficient discomfort and interferes with normal everyday activities.
- **Severe:** An event that prevents normal everyday activities. An AE that is assessed as severe should not be confused with an SAE. Severe is a category utilized for rating the intensity of an event; and both AEs and SAEs can be assessed as severe.

An event is defined as “serious” when it meets at least 1 of the predefined outcomes as described in the definition of an SAE, NOT when it is rated as severe.

Assessment of Causality

- The investigator is obligated to assess the relationship between study intervention and each occurrence of each AE/SAE.
- A “reasonable possibility” of a relationship conveys that there are facts, evidence, and/or arguments to suggest a causal relationship, rather than a relationship cannot be ruled out.
- The investigator will use clinical judgment to determine the relationship.
- Alternative causes, such as underlying disease(s), concomitant therapy, and other risk factors, as well as the temporal relationship of the event to study intervention administration, will be considered and investigated.
- The investigator will also consult the IB and/or product information, for marketed products, in his/her assessment.
- For each AE/SAE, the investigator **must** document in the medical notes that he/she has reviewed the AE/SAE and has provided an assessment of causality.
- There may be situations in which an SAE has occurred and the investigator has minimal information to include in the initial report to the sponsor. However, **it is very important that the investigator always make an assessment of causality**

for every event before the initial transmission of the SAE data to the sponsor.

- The investigator may change his/her opinion of causality in light of follow-up information and send an SAE follow-up report with the updated causality assessment.
- The causality assessment is one of the criteria used when determining regulatory reporting requirements.
- If the investigator does not know whether or not the study intervention caused the event, then the event will be handled as “related to study intervention” for reporting purposes, as defined by the sponsor. In addition, if the investigator determines that an SAE is associated with study procedures, the investigator must record this causal relationship in the source documents and CRF, and report such an assessment in the dedicated section of the CT SAE Report Form and in accordance with the SAE reporting requirements.

Follow-up of AEs and SAEs

- The investigator is obligated to perform or arrange for the conduct of supplemental measurements and/or evaluations as medically indicated or as requested by the sponsor to elucidate the nature and/or causality of the AE or SAE as fully as possible. This may include additional laboratory tests or investigations, histopathological examinations, or consultation with other healthcare providers.
- If a participant dies during participation in the study or during a recognized follow-up period, the investigator will provide Pfizer Safety with a copy of any postmortem findings including histopathology.
- New or updated information will be recorded in the originally completed CRF.
- The investigator will submit any updated SAE data to the sponsor within 24 hours of receipt of the information.

10.3.4. Reporting of SAEs

SAE Reporting to Pfizer Safety via an Electronic Data Collection Tool

- The primary mechanism for reporting an SAE to Pfizer Safety will be the electronic data collection tool.
- If the electronic system is unavailable, then the site will use the paper SAE data collection tool (see next section) in order to report the event within 24 hours.
- The site will enter the SAE data into the electronic system as soon as the data become available.
- After the study is completed at a given site, the electronic data collection tool will be taken off-line to prevent the entry of new data or changes to existing data.
- If a site receives a report of a new SAE from a study participant or receives updated data on a previously reported SAE after the electronic data collection tool has been taken off-line, then the site can report this information on a paper SAE form (see next section) or to Pfizer Safety by telephone.

SAE Reporting to Pfizer Safety via CT SAE Report Form

- Facsimile transmission of the CT SAE Report Form is the preferred method to transmit this information to Pfizer Safety.
- In circumstances when the facsimile is not working, notification by telephone is acceptable with a copy of the CT SAE Report Form sent by overnight mail or courier service.
- Initial notification via telephone does not replace the need for the investigator to complete and sign the CT SAE Report Form pages within the designated reporting time frames.

10.4. Appendix 4: Contraceptive Guidance

10.4.1. Male Participant Reproductive Inclusion Criteria

Male participants are eligible to participate if they agree to the following requirements during the intervention period and for at least 3 days after the last dose of study intervention, which corresponds to the time needed to eliminate reproductive safety risk of the study intervention(s):

- Refrain from donating sperm.

PLUS either:

- Be abstinent from heterosexual intercourse with a female of childbearing potential as their preferred and usual lifestyle (abstinent on a long-term and persistent basis) and agree to remain abstinent.

OR

- Must agree to use a male condom when engaging in any activity that allows for passage of ejaculate to another person.

In addition to male condom use, a highly effective method of contraception may be considered in WOCBP partners of male participants (refer to the list of highly effective methods below in [Section 10.4.4](#)).

10.4.2. Female Participant Reproductive Inclusion Criteria

A female participant is eligible to participate if she is not pregnant or breastfeeding, and at least 1 of the following conditions applies:

- Is not a WOCBP (see definitions below in [Section 10.4.3](#)).

OR

- Is a WOCBP and using a contraceptive method that is highly effective (with a failure rate of <1% per year), as described below, during the intervention period and for at least 28 days after the last dose of study intervention, which corresponds to the time needed to eliminate any reproductive safety risk of the study intervention(s). If a highly effective method that is user dependent is chosen, a second effective method of contraception, as described below, must also be used. The investigator should evaluate the effectiveness of the contraceptive method in relationship to the first dose of study intervention.
- The investigator is responsible for review of medical history, menstrual history, and recent sexual activity to decrease the risk for inclusion of a woman with an early undetected pregnancy.

10.4.3. Woman of Childbearing Potential

A woman is considered fertile following menarche and until becoming postmenopausal unless permanently sterile (see below).

If fertility is unclear (eg, amenorrhea in adolescents or athletes) and a menstrual cycle cannot be confirmed before the first dose of study intervention, additional evaluation should be considered.

Women in the following categories are not considered WOCBP:

- Premenopausal female with 1 of the following:
 - Documented hysterectomy.
 - Documented bilateral salpingectomy.
 - Documented bilateral oophorectomy.

For individuals with permanent infertility due to an alternate medical cause other than the above, (eg, mullerian agenesis, androgen insensitivity), investigator discretion should be applied to determining study entry.

Note: Documentation for any of the above categories can come from the site personnel's review of the participant's medical records, medical examination, or medical history interview. The method of documentation should be recorded in the participant's medical record for the study.

- Postmenopausal female:
 - A postmenopausal state is defined as no menses for 12 months without an alternative medical cause. In addition, a
 - High FSH level in the postmenopausal range must be used to confirm a postmenopausal state in women under 60 years of age and not using hormonal contraception or HRT.
 - Female on HRT and whose menopausal status is in doubt will be required to use one of the nonestrogen hormonal highly effective contraception methods if they wish to continue their HRT during the study. Otherwise, they must discontinue HRT to allow confirmation of postmenopausal status before study enrolment.

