		
hormonal therapy as contraception method or as replacement therapy to manage post-menopausal symptoms.
 
Rationale: Hormones used for female contraception or as replacement therapies may increase the risk of developing thrombotic events.
 
• Sections Impacted: Section 3: Objectives, Estimands, and Endpoints Section 9.4.2. Secondary Endpoint: Pharmacokinetic Analyses 
Change: Plasma PK parameters from Part 1 updated. Only C24 and C24 (dn) will be reported.
 
Rationale: Due to reduced PK sampling in Part 1, some PK parameters cannot be accurately estimated, therefore, not reported.
 
This amendment is making the following non substantial changes:
 
• Sections Impacted• Section 1.3: Schedule of Activities (Part 1 and Part 2)• Section 8.2.3: Electrocardiograms 
Change: Added additional time window for ECG assessments.
 
• Sections Impacted: Section 1.2: Schema Section 4.1.1: Overall Design Part 1: SAD 
Change: Changed 1.0-fold to 1-fold
 
• Section 2.2.2: Clinical Overview 
Change: Changed the sentence from “The study is planned to begin in Oct-2020” to “The study began in Oct-2020” to align with the Amendment date.

Amendment	16 October	This amendment is making the following substantial

2	2020	
changes:
 
• Sections Impacted: Section 1.3: SoA Table Section 8: Study Assessments and Procedures Change:
i. Removed PK blood draws at 0.5 hr, 26 hr, and 30 hr and made 2 hr PK blood draw optional in Part 1: SAD (24-h infusion).ii. Made 6 hr blood draws for selected biomarkers (including plasma PD biomarker, serum PD biomarker, and banked biospecimen [Prep D1]) optional in Part 1: SAD (24-h infusion).iii. Removed biomarker blood collection for specified viral genetics in Part 1: SAD (24-h infusion) and Part 2: Extended Infusion (120-h infusion).iv. Removed 12-lead triplicate ECG assessments at 0.5 hr and 2 hr timepoints in Part 1: SAD (24-h infusion).• Sections Impacted: Protocol Title Section 1: Protocol Summary (Synopsis) Section 2: Introduction Section 4: Study Design Section 5: Study Population 
Change: Broadened the inclusion range of patient severity by allowing patients with severe symptoms of COVID-19, with some limitations.
 
• Removed exclusion criterion #1d.
---	------	---

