- j. Administration starts on Day 1 and continues for 24 hours and ends on Day 2. **Sentinel dosing will be used in each dose-escalating cohort.** A small cohort of 2 participants (1 receiving PF-07304814 and 1 receiving placebo) will be dosed prior to the remainder of the cohort. All available safety and tolerability data from the 2 sentinel participants up to Day 3 at 24 hours post completion of dosing will be reviewed by the Investigator(s) (if available), the study team and IRC. The independent IRC will then determine whether it is safe to proceed to dose the remaining participants in the cohort.

k. For discharged participants, Days 6 and 30-37 should be conducted at the clinical site. However, if this is not possible, the visit may be conducted by phone in which case only clinical data (AE, **CCI** [REDACTED] concomitant medications) and contraception check will be obtained. (If available, kits to assess viral load to be provided for at-home specimen collection in the instance that a visit is conducted by telephone, and arrangements may be made to collect blood samples for clinical chemistry and/or hematology).

[REDACTED]

[REDACTED]

PART 2: MAD (120-h infusion)

Visit Identifier	Screening Days -3 to 1	Treatment Day 1	Treatment Days 2-5	End of Treatment Day 6	Follow-up 1 (Day 7)	Follow-up 2 (Day 10) ^l ±1 day	Follow-up 3 (Day 14) ^l ±2 days	Follow-up 4 (Day 34-41) ^l	Early Termination
Planned Hours Post Start of Infusion		pre-Dose	24h (Day 2), 48h (Day 3), 72h (Day 4), 96h (Day 5)	120h					
ELIGIBILITY									
Informed consent	X								
Verify inclusion/exclusion criteria ^a	X								
Demographics & Medical history	X								
Required Confinement		X	→	→	X				
PHYSICAL EXAMINATION & ECG & VITALS									
Complete physical examination	X			X					X
Targeted physical examination		X	X		X	X	X	X	
Supine vital signs (temperature, pulse rate, blood pressure, respiratory rate)	X	X	X	X	X	X	X	X	X
Pulse oximetry/SpO ₂	X	X	X	X	X	X	X	X	X
Weight, Height	X								
12-Lead ECG ^b	X	X	Day 2, 3, 5 only	X	X	X	X	X	X
LABORATORY									
Hematology ^c	X	X	Day 2, 3, 5 only	X	X	X	X	X	X
Blood chemistry ^c	X	X ^d	Day 2, 3, 5 only	X ^d	X	X	X	X	X
Coagulation Panel (PT, aPTT, D-dimer) and Fibrinogen		X	Day 2, 3, 5 only	X	X	X	X	X	X
Urinalysis ^c	X	X	Day 3 only	X	X	X	X	X	X
FSH (to confirm post-menopausal status)	X								
Pregnancy test (WOCBP only)	X ^{c,e}						X		
CCI									
SARS-CoV-2 Viral load Assessments ^f	X	X	Day 3 only	X	X	X	X	X	X

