12. Participant is receiving any medications or substances that are strong inhibitors or inducers of cytochrome P450 (CYP) 3A4.
13. Participant has received systemic oral, intravenous, or intramuscular corticosteroid therapy (>40 mg/day equivalent prednisolone) within the previous 28 days, except as required for COVID-19 treatment.
14. Female participant who are taking hormonal therapy for contraception or as estrogen replacement therapy, post menopause.

Prior/Concurrent Clinical Study Experience:

15. Previous administration with any investigational drug within 30 days (or as determined by the local requirement) or 5 half-lives preceding the first dose of investigational product used in this study (whichever is longer).

Note: Participants are allowed to participate if receiving local standard of care for COVID-19 including Remdesivir, convalescent sera/plasma, monoclonal antibody treatments. Participation in an open-label investigational/observational study for convalescent serum/plasma is also allowed so long any associated study procedures do not, in the opinion of the investigator, interfere with the current study. If other therapies receive Emergency Use Authorization status, they may also be allowed after discussion with the sponsor.

Diagnostic Assessments:

16. Screening 12-lead ECG that demonstrates clinically relevant abnormalities that may affect participant safety or interpretation of study results (eg, baseline QTcF interval >450 msec, complete LBBB, signs of an acute or indeterminate-age myocardial infarction, ST-T interval changes suggestive of myocardial ischemia, second- or third-degree AV block, or serious brady-arrhythmias or tachyarrhythmias).
 - If QTcF exceeds 450 msec, or QRS exceeds 120 msec, the ECG should be repeated 2 more times and the average of the 3 QTcF or QRS values should be used to determine the participant's eligibility. Computer-interpreted ECGs should be overread by a physician experienced in reading ECGs before excluding participants.
17. Participants with any of the following abnormalities in clinical laboratory tests at screening, confirmed by a single repeat test, if deemed necessary:
 - AST or ALT level ≥ 3 times the ULN.
 - Total bilirubin level ≥ 1.5 times the ULN, unless due to known Gilbert's syndrome.
 - $CL_{cr} < 60$ mL/min using the Cockcroft-Gault equation.
 - Absolute neutrophil count $< 1000/\text{mm}^3$.

Other Exclusions:

18. Females who are pregnant or breastfeeding.

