6.5. Concomitant Therapy

Medications taken prior to dosing will be documented as prior medications. Medications taken after the first dose of study intervention has been administered will be documented as concomitant medications. All concomitant medications taken during the study must be recorded in study records with indication, daily dose, and start and stop dates of administration. Participants will be queried about concomitant medication (including topical medications and treatments, over-the-counter and prescription medications and treatments, herbals, and vaccinations) at each visit. Any new concomitant medications or dose changes to current concomitant medications should be evaluated for potential new or worsening adverse events.

Study intervention is to be administered on top of SoC for this study. It is recognized that SoC may change during the course of the study, and it is therefore important to meticulously capture all SoC in the CRF.

Prohibited medications are shown in [Appendix 8: Prohibited Medications](#).

Hormonal therapy for purposes of contraception or postmenopausal replacement therapy will not be allowed to be used in participants (see [Appendix 4: Contraceptive Guidance](#)).

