10.4.4. Contraception Methods

Contraceptive use by men or women should be consistent with local availability/regulations regarding the use of contraceptive methods for those participating in clinical trials. Female participants utilizing hormonal contraception, including those with hormonal intrauterine devices placed, cannot participate in the study since hormonal contraception is not permitted.

Highly Effective Methods That Have Low User Dependency

1. Non hormonal intrauterine device
2. Bilateral tubal occlusion.
3. Vasectomized partner:
 - Vasectomized partner is a highly effective contraceptive method provided that the partner is the sole sexual partner of the woman of childbearing potential and the absence of sperm has been confirmed. If not, an additional highly effective method of contraception should be used. The spermatogenesis cycle is approximately 90 days.
- **Highly Effective Methods That Have Low User Dependency**
4. Sexual abstinence:
 - Sexual abstinence is considered a highly effective method only if defined as refraining from heterosexual intercourse during the entire period of risk associated with the study intervention. The reliability of sexual abstinence needs to be evaluated in relation to the duration of the study and the preferred and usual lifestyle of the participant.

CCI

CCI

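### Section 10.4.3 lets some women continue HRT with a hormonal contraceptive, which exclusion 14 and Sections 6.5 and 10.4.4 do not permit

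*Protocol*

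**What the plan says.** The last bullet of Protocol Section 10.4.3 deals with a woman on hormone replacement therapy (HRT) whose menopausal status is uncertain, and gives her two routes. The first reads: "Female on HRT and whose menopausal status is in doubt will be required to use one of the nonestrogen hormonal highly effective contraception methods". The bullet applies this route to such women "if they wish to continue their HRT during the study". The second is to stop HRT so that postmenopausal status can be confirmed before she is enrolled.

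Three other places in the current protocol address hormonal therapy:

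- Section 5.2, exclusion 14, excludes: "Female participant who are taking hormonal therapy for contraception or as estrogen replacement therapy, post menopause".
- Section 6.5 states: "Hormonal therapy for purposes of contraception or postmenopausal replacement therapy will not be allowed to be used in participants". The same sentence points the reader to Appendix 4, which contains Section 10.4.3.
- Section 10.4.4 opens with: "Female participants utilizing hormonal contraception, including those with hormonal intrauterine devices placed, cannot participate in the study since hormonal contraception is not permitted".

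The amendment history gives the sponsor's reason under Amendment 3: "Hormones used for female contraception or as replacement therapies may increase the risk of developing thrombotic events". It is cited here only for that reason. The conflict itself lies between sections of the current text.

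**The concern.** The first route in 10.4.3 makes use of a hormonal contraceptive the condition for staying on HRT. The protocol excludes women who use hormonal contraception, and it does not allow postmenopausal replacement therapy during the study. A site that took the bullet at its word would enrol a participant who meets an exclusion criterion. Sections 5 and 8 do not permit waivers, so that would be a protocol deviation.

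What is at stake is participant safety. The sponsor added the hormonal ban because hormones may raise thrombotic risk, and Section 2.2 describes hospitalized COVID-19 patients as already at increased risk of thromboembolic events. The bullet allows both a hormonal contraceptive and continued HRT, so it undoes the ban for the subgroup it describes.

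**Working it through.** No arithmetic applies. The check sets the two parts of the 10.4.3 option against each section that governs hormonal therapy.

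| Section | Hormonal contraceptive | Continued HRT |
|---|---|---|
| 10.4.3, first route | required | allowed |
| 5.2, exclusion 14 | barred | barred for estrogen replacement after menopause |
| 6.5 | barred | barred as postmenopausal replacement |
| 10.4.4 | barred | not addressed |

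**Step 1: the contraceptive part.** All three sections bar hormonal contraception, and none makes an exception for nonestrogen products. The four methods visible in 10.4.4 are a non-hormonal intrauterine device, bilateral tubal occlusion, a vasectomized partner and abstinence. None is hormonal. Redacted material follows that list, so its completeness cannot be confirmed. The conclusion does not need the list, because the opening statement of 10.4.4 excludes users of hormonal contraception whatever follows it.

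**Step 2: the HRT part.** Section 6.5 gives the wider bar, covering postmenopausal replacement therapy generally. Exclusion 14 reaches only estrogen replacement, and 10.4.4 says nothing about HRT. Both HRT bars are worded for women after menopause, whereas the bullet concerns women whose status is in doubt. A site could therefore argue that neither HRT bar clearly applies to her, while 10.4.3 names her case directly. The contraception bars apply to her either way.

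**Step 3: an alternative reading.** Suppose the phrase nonestrogen hormonal was meant loosely, as ruling out estrogen-containing hormonal methods without requiring a hormonal one. The contraceptive conflict would then disappear. Continued HRT would still conflict with 6.5 and, for estrogen products, with exclusion 14. The reading is strained, and the wording would need correcting in any case.

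**Step 4: whether sites use this text.** Inclusion criterion 1 (Section 5.1) refers to 10.4.2 for female participants. The first qualifying condition in 10.4.2 is "Is not a WOCBP (see definitions below in" Section 10.4.3. Section 6.5 also refers to Appendix 4 in the sentence that states the ban. The bullet is therefore operative eligibility text.

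**Step 5: whether the second route is workable.** Stopping HRT before enrolment is consistent with all the bans. The time available is short: the Schedule of Activities heads the screening column "Screening Days -3 to 1". FSH is scheduled only at screening (Section 1.3 and Table 10), and 10.4.3 sets no interval between stopping HRT and confirming status. Confirmation may not be possible in time, and the bullet does not say what happens then.

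**The case against.** The strongest reply is that the protocol already prevents harm. Under Section 5.2 any single exclusion is enough to keep a participant out. Exclusion 14 names hormonal contraception, Section 6.5 repeats the ban, and waivers are not permitted. A site sent to 10.4.3 must go on to 10.4.4 to select a method, and the prohibition stands at the top of that section. The same bullet also offers a compliant route, which is to stop HRT. On this view the bullet is leftover wording, and the correction is editorial.

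Most of this stands. Exclusion 14 and 6.5 should block enrolment, only the first of the two routes is defective, and the affected group is narrow in a study of about 72 participants at most. The reply does not remove the conflict. No sentence says which section governs when they disagree, and the bullet is the text that addresses this woman's case most specifically.

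Two objections concern the proposed wording. First, making all women on HRT ineligible goes further than exclusion 14, which names only estrogen. That is correct, but it matches the wider bar in 6.5. Second, the fallback to childbearing-potential status is already implied, because 10.4.3 treats a woman as fertile until she is postmenopausal or permanently sterile. That is also correct. The fallback clarifies the existing rule, and stating it is useful given the short screening window.

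**Conclusion.** The concern holds. On hormonal contraception, one bullet in 10.4.3 contradicts three sections (5.2, 6.5 and 10.4.4). On HRT it contradicts two: 6.5, and 5.2 for postmenopausal estrogen. No participant can take the first route and still comply with the protocol.

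The three-section count assumes the ordinary reading of the bullet, that a hormonal contraceptive is required. On the looser reading only the HRT conflict remains.

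The practical risk is confined to a site that relies on this bullet for a woman on HRT with doubtful menopausal status, and the documents give no basis for estimating how many there would be. No endpoint, sample size or analysis is affected. The bullet should be corrected because it is an eligibility rule that is wrong as written, on a safety restriction.

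**What to change.** In Section 10.4.3, delete the option to continue HRT with a nonestrogen hormonal contraceptive and replace the bullet with:

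> Women on HRT are not eligible unless HRT is discontinued before enrolment. If postmenopausal status is not then confirmed, the participant is treated as a WOCBP and must use a non-hormonal method from Section 10.4.4.

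Exclusion 14, Section 6.5 and Section 10.4.4 stay as they are. A shorter edit, deleting the first route and keeping the existing sentence on stopping HRT, would also remove the contradiction. It would leave unstated what to do when status cannot be confirmed during screening.

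The cost is one edited bullet in Appendix 4, with no change to procedures, sample size or analysis.
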